## 6.2. Analysis Plan

For **Aim 1**, we will use covariate balancing propensity scoring based on the CBPS package in R [28] to create comparable (balanced) groups based on their risk factor (covariate) profile in subjects according to their propensity (probability) to move from conservative management to liver transplantation. This approach leads to a model that predicts treatment assignment (conservative vs. liver transplantation) and balances covariates, especially those related to study outcome(s), and offers the best opportunity to simulate RCT results from observational data. From prior experience, many through the UCDC [26,31,32], we know many of the important risk factors, which include neonatal vs. late onset, number of prior hyperammonemic events, event severity in terms of hyperammonemic coma score [2], ammonia and glutamine levels at regularly scheduled clinic visits, and duration from birth to transplant or index date. In addition to these, we will consider comorbidities, organ function, and other laboratory assessments. The CBPS software will help us choose the model that maximizes covariate balance and generate the CBPS for each participant. The next steps will be to order the dataset according to the CBPS. It is useful at this point to select CBPS to cut points to form homogeneous strata to assess the number of subjects with a liver transplant and conservative management per stratum. Those strata where there are

insufficient numbers (mismatches) of conservative treatment or liver transplant subjects will be described, documented and excluded from the primary analysis due to lack of covariate balance. Before conducting model-based analyses for **Aim 1**, we will compare survival times based on the log-rank test in Kaplan-Meier analysis and the difference between mean scores based on t-tests by treatment for neurodevelopment and quality of life within each stratum to evaluate evidence of heterogeneity. Evidence of heterogeneity will provide clues to interactive effects based on UCD severity which will be modeled in regression analyses below by including a cross products term of treatment type with CBPS. Based on these results, we will develop general linear random effects longitudinal regression models in STATA 14

[<http://www.stata.com/stata14/>] to perform analysis of covariance that will enable us to evaluate **Aim 1** outcomes of neurodevelopment and quality of life. Each model will include treatment type, the baseline measurement of each outcome, as well as the CBPS and if necessary the cross product of treatment type by CBPS. When we address survival, we will implement Cox Regression models to predict survival time by treatment and will either control for CBPS or stratify on it in the case of heterogeneity.

We used PASS 12 [33] to evaluate statistical power to address study aims for sample sizes per group (liver transplantation vs. conservative management) of 90 and 80 in 2-tailed testing at an alpha of 0.05, which assumes some losses in the sample entering analysis in order to maintain adequate covariate balance between groups. For neurodevelopmental and quality of life assessments, we have 80% power to detect modest 0.4sd effect size differences between groups assuming two repeated measurements per person correlated at 70% (ICC). For mortality, assuming the rate in the conservatively treated group remains about 28%, the study will have 80% power to detect and increase in the liver transplant group of about 60% which is robust to differences in sample size between 80 and 90 per group. The study is well powered to detect any clinically meaningful difference in neurocognitive outcomes and QOL and adequately powered to detect a moderate difference in mortality between groups.

For **Aim 2**, interview data will be managed using QSR International NVivo 10 software [[http://www.qsrinternational.com/products\\_nvivo.asp](http://www.qsrinternational.com/products_nvivo.asp)], a program that allows us to collect, organize, and code qualitative data sources. Although not explicitly a grounded theory study, our approach to the analysis of primary caretaker and provider interview data will borrow from aspects of Strauss and Corbin's systematic procedures for grounded theory work [34]. No existing framework or theory currently exists that describes the process which UCD patients and their families undertake when making the difficult decision to pursue liver transplant or continue conservative management. Thus, some of Strauss and Corbin's analysis techniques are suitable for this study aim, which seeks to describe a process/experience in a field where there is little pre-existing evidence.

Initial data abstraction will be conducted through the line-by-line open coding of a cross-section of 10-15 primary caretaker and provider interview transcripts. This will allow key issues regarding the liver transplant vs. conservative management decision-making process to emerge directly from the collected data and will ensure that important aspects of this phenomenon are not precluded through the use of a more selective

coding schema. We will use this initial process of open coding to generate a preliminary set of codes, which will be continuously refined via team consensus (i.e. merged, modified, and reduced) until a final structure of codes and sub-codes emerges. This coding structure will then be applied systematically across all interview transcripts, employing thematic content analysis to categorize data into recurrent or common themes [35].

Thematic content analysis will form the basis of our more sophisticated interpretation, which will move beyond a typology of participant accounts to look at the relationship between the themes we've identified and to build a framework that describes how primary caretakers of pediatric patients with UCD, their families, and their providers reach a shared treatment decision and the key clinical, social, and/or system level factors that influence this process. Our stratified purposive sampling strategy will allow us to examine differences and similarities among sub-populations of patients and their families in terms of how they experience this decision process. This will help facilitate the identification of issues that are common across groups as well as the factors that create differences in the way patients and families approach/experience this decision. To facilitate this level of analysis, we will employ common framework analysis techniques such as charting (i.e. reorganizing data according to thematic content in side-by-side charts to visualize/compare a range of perspectives across cases) and mapping and interpretation (i.e. using diagrams and tables to physically explore the relationship between themes) [35]. A team of 2-3 researchers will be used to code all interview data and inter-rater reliability scores will be calculated to assess agreement between coders. Members of the research team will code data independently but will collaborate to reach consensus on coding definitions as well as emerging key themes and the relationships between them.

For **Aim 3**, focus group data will be analyzed using thematic content analysis (see description above) to validate the decision-making framework developed through **Aim 2** and to identify key opportunities for improved dissemination of evidence-based information to families of UCD patients including when information should be delivered, who should deliver it, how it should be delivered, and what additional supports should be provided to improve the families' experience as they navigate the difficult decision to pursue liver transplant or continue conservative management. Focus group and interview data findings will be used in conjunction to draft a dissemination strategy that is responsive to the expressed needs of patients and their families, that aligns with the decision-making process illustrated through **Aim 2**, and that makes use of patient-preferred mechanisms of communication. Focus group participants will also be asked to provide feedback on portions of this dissemination strategy as it is being developed. Focus group data will also be managed using QSR International NVivo 10 software and coded by a team of 2-3 researchers as described above.

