### **3.3.2. Liver Transplantation and Outcome**

Liver transplantation for UCD patients was initiated in the early 1990's, before alternate pathway medical therapy was widely available. There were anecdotal case reports of liver transplantation in four of the urea cycle disorders (CPSD, OTCD, ASD, and ALD) [13, 15, 22]. A larger survey of 16 US patients who had received liver transplants from four major transplant centers found that 14 of these cases had survived at least 1-6 years [14]. Their neurological status post-transplantation was in most cases moderately to severely impaired and correlated closely with their condition prior to transplantation. However, the quality of their lives seemed to have improved. Subsequently, to determine if aggressive medical therapy could improve the outcome of severe infantile onset UCD, 5 such cases were monitored at Baylor College of Medicine before and after liver transplantation, including 2 males with OTCD, 2 with CPSD, and one female with OTCD deficiency and intractable hyperammonemia [23]. Three of these infants had serial developmental testing (Griffiths scale) before and after transplantation. It was found that their pre-transplantation overall developmental scales (51, 86, 56) were stabilized after transplantation (70-83, 80-76, 51-47, respectively). Therefore, the authors recommended that early transplantation be considered as the treatment of choice in these severely affected infants.

Most recently, a retrospective analysis of 186 patients with UCD who underwent liver transplantation, [24] showed an increased frequency of liver transplantation for UCD and organic acidemia over the last decade, with 5-year survival rates of 88-99% depending on age. In summary, liver transplantation is now performed frequently to treat UCD and survival seems to have improved over time. However, the outcome of neurocognitive function following liver transplantation is unclear, and it is unknown how it compares to conventional conservative management.

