### **3.3.3. The Process of Making UCD Treatment Decisions**

Despite the importance of and complexity surrounding the decision to continue conservative management or consider liver transplant in UCD, no research has been conducted to date on how primary caretakers of pediatric UCD patients make these treatment choices and the issues that influence their decision to pursue one option over another. Some existing research investigating parent decision making in

pediatric treatments has been published in other disease areas such as end-of-life care, cardiac transplantation, lung transplant in patients with cystic fibrosis, and cancer treatment. A 2012 narrative review of the current research on parent decision making about pediatric treatment found that in addition to consulting their provider, most parents consider their child's health status, the perspectives of other members of their community, their prior knowledge, and other personal factors such as emotions and faith when making treatment decisions for their child [25]. Although the findings from these studies can help inform our understanding of the treatment decision-making process among the caretakers of pediatric patients with UCD, the characteristics of this disease group and the risks associated with its treatment options vary in several important ways from other disease areas, effectively limiting the applicability of these previous studies in this population. One of the most critical differences concerns the acuteness and unpredictable nature of severe hyperammonemia episodes, which carry the risk of death or increased neurocognitive dysfunction. Even if a patient's condition appears to be amenable to conservative management, he or she is still susceptible to acute hyperammonemia during incurrent infections or while experiencing other stressors. This "ticking bomb" phenomenon is factored in the treatment decision of patients on whether pursuing liver transplant, thus increasing the need for better research that focuses specifically on the experience of making treatment decisions by the UCD population.

[figure not shown]

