###### **Historical Data:**

- Eligibility
- Enrollment/demographic information
- Review of past medical records, including:
  - growth charts
  - neurodevelopmental testing
  - neurological evaluation
  - biochemical and diagnostic testing (e.g., ammonia, plasma amino acids, DNA sequencing of UCD genes)

- history of hospitalizations
- medications and other treatments (e.g., dialysis)
- other comorbidities

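### Pre-transplant neurological and developmental state is not a named propensity covariate, and the baseline used in the outcome models is not dated before transplant

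*Combined protocol and SAP*

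**What the plan says.** Section 6.2 builds a covariate-balancing propensity score (CBPS) for moving from conservative management to transplant, and gives priority to covariates tied to outcome. The risk factors it names are onset type, the count of earlier hyperammonemic events, coma score, routine ammonia and glutamine values, and the time from birth to transplant or index date. It adds: "In addition to these, we will consider comorbidities, organ function, and other laboratory assessments".

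The score is then used in three ways:
- It defines strata. Strata with too few children in one group are left out of the primary analysis.
- Within strata, survival is compared by log-rank test and mean scores by t-test.
- It enters the outcome models. The neurodevelopment and quality-of-life models also contain the baseline value of the outcome. The Cox model controls for the score or is stratified on it.

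On the importance of prior state, section 3.3.2 says of a survey of 16 transplanted patients: "Their neurological status post-transplantation was in most cases moderately to severely impaired and correlated closely with their condition prior to transplantation". On availability, the historical data in section 4.5 include "neurodevelopmental testing" and "neurological evaluation", listed apart from other comorbidities.

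**The concern.** A child's neurological and developmental state before treatment is an obvious candidate confounder for later IQ/DQ. If it differs between the groups after balancing on the named covariates, part of that difference will be read as an effect of transplantation.

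The named covariates cover it only in part. Coma score and number of events are proxies for brain injury. Section 3.3.1 reports that poor cognitive outcome in the consortium's own cohort was not fully explained by age of onset, peak ammonia or length of the first admission.

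The baseline term would close most of the gap in the neurodevelopment and quality-of-life models if it preceded transplant. The plan does not say that it does. Section 4.5 describes baseline as a study visit, sections 4.3 and 4.4 describe two testing visits, and section 6.1 expects 92 children to have received a transplant. For a child enrolled after surgery, a score from the study visit is a post-treatment measurement. Adjusting for it leaves some confounding in place and can also remove a real effect.

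**Working it through.** **Inputs from section 6.2.** Target difference 0.4 SD; 80 to 90 per group; two measurements per child with correlation 0.7; two-sided alpha 0.05; 80% power.

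**The plan's own figure.** The SD of the mean of two measurements is √((1 + 0.7)/2) = 0.922. With 90 and 80 children, SE = 0.922 × √(1/90 + 1/80) = 0.142, which gives 80.6% power for 0.4 SD. With 80 per group it is 78.3%. The stated 80% reproduces.

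**Bias with no adjustment for prior state.** Let d be the gap in prior state between groups (in SD) and r its correlation with the later score. Then bias ≈ r × d. The documents give neither value, so both are assumed. The plan's 0.7 describes two study measurements and is borrowed here only as a middle value for r. Each cell shows the bias in SD and, in brackets, how often a true null is rejected with 80 per group (SE = 0.922 × √(2/80) = 0.146).

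| r | d = 0.2 | d = 0.3 | d = 0.5 |
|---|---|---|---|
| 0.5 | 0.10 (10.5%) | 0.15 (17.7%) | 0.25 (40.3%) |
| 0.7 | 0.14 (16.1%) | 0.21 (30.2%) | 0.35 (67.0%) |
| 0.9 | 0.18 (23.5%) | 0.27 (45.7%) | 0.45 (87.0%) |

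At r = 0.7 and d = 0.2 to 0.3, the bias is 0.14/0.4 = 35% to 0.21/0.4 = 52% of the target. Here d should be read as the gap that remains after balancing on the named covariates. Because those covariates are partly correlated with prior state, r = 0.7 probably overstates what is left.

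**Bias with a baseline term.** This was simulated with 85 per group, 4,000 runs, r = 0.7, correlation 0.7 between enrolment and follow-up scores, and one follow-up score. Transplanted children start lower by d, a sign chosen only for illustration. Any true effect is assumed to be fully present at enrolment. Entries are the estimated effect in SD, with the rejection rate where the true effect is zero.

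| True effect | d | No baseline term | Pre-transplant baseline | Enrolment baseline, after transplant |
|---|---|---|---|---|
| 0 | −0.3 | −0.21 (26.8%) | 0.00 (5.4%) | −0.06 (8.3%) |
| 0 | −0.5 | −0.35 (61.7%) | 0.00 (4.6%) | −0.11 (15.8%) |
| 0.4 | −0.3 | 0.19 | 0.40 | 0.06 |
| 0.4 | −0.5 | 0.06 | 0.40 | 0.02 |

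The last column follows from algebra. Enrolment and follow-up scores carry the same group gap, so the adjusted estimate is (1 − 0.7) × (r × d + true effect). For d = −0.5 and a true effect of 0.4 this is 0.3 × (−0.35 + 0.40) = 0.015. Of that, 0.3 × 0.40 = 0.12 is what survives of the true effect and 0.3 × (−0.35) = −0.105 is leftover confounding.

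**Which analyses are exposed.**
- Strata, exclusions and Cox model: they depend on the score alone, so prior state is not addressed unless it is in the score.
- Within-stratum t-tests: no baseline term, and fewer children than in the first table.
- Neurodevelopment and quality-of-life models: protected if baseline precedes transplant or index date; not protected if it follows transplant.

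**The case against.** The strongest reply is that the plan already adjusts for prior state where it matters most. The neurodevelopment and quality-of-life models contain the baseline value, historical testing is gathered at the baseline visit, and children followed in the Longitudinal Study may have been tested before surgery. This stands in part: with a true pre-transplant baseline, the simulated bias is zero. But the plan does not define baseline that way, and the term is absent from the other analyses.

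The covariate list is also open-ended, and documented developmental delay might be recorded as a comorbidity. That would permit the adjustment without committing to it.

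Four stronger readings are tempting and are not supported:
- *That 0.14 to 0.21 SD is the expected error of the planned models.* It describes a comparison with no adjustment for prior state and rests on assumed r and d.
- *That prior state determines outcome.* Section 3.3.2 reports a correlation in 16 patients, with no coefficient.
- *That prior state is shown to drive the choice of transplant.* Section 3.3.3 says "most parents consider their child's health status", but this comes from a review of other conditions whose applicability to UCD the same section calls limited. Health status is also broader than neurological state.
- *That prior state is a documented predictor of death or quality of life.* No section says so. Section 3.3.2 reports that quality of life seemed to improve despite impairment, and section 3.3.4 attributes mortality and morbidity to hyperammonemia and surgical complications.

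**Conclusion.** The point holds in this form and should be fixed. A covariate that the protocol itself reports as closely related to neurological outcome, and plans to collect, is missing from the propensity specification. The one term that could stand in for it is not dated relative to transplant.

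The size is conditional. Where prior state is unadjusted, assumed r of 0.5 to 0.9 and d of 0.2 to 0.5 SD give a bias of 0.10 to 0.45 SD against a 0.4 SD target. With a pre-transplant baseline, the bias in the neurodevelopment model disappears in the simulation. With a post-transplant baseline, 30% of the confounding remains and, if the effect is already present at enrolment, only 30% of a true effect survives. The 30% is 1 − 0.7 and rests on the assumed correlation.

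The direction cannot be settled from the documents. Table 2 shows a severity difference (peak ammonia above 200 in 98% versus 74%) but gives no developmental scores. No size can be given for survival.

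**What to change.** In section 6.2:

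1. Add two covariates to the score, each dated before transplant or index date: the last neurological evaluation, and the last developmental level (IQ/DQ if tested, otherwise documented delay recorded as yes, no or unknown). Report balance on both before any outcome is analysed. This carries them into the strata and the CBPS-adjusted Cox model.
2. Define the baseline measurement in the outcome models as the last value before transplant or index date, and do not use a post-transplant score as baseline.
3. Add a sensitivity analysis restricted to children whose state before transplant or index date is known. An unknown category balances missingness, not brain injury.

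The cost is mainly wording, plus abstraction from records that section 4.5 already plans to review. Section 6.2 uses an index date without defining it, so that date must be stated. The main downside is missing data. Table 2 gives surgery age as 11.7 months (1.5 to 186, which I read as median and range), and Table 1 has no IQ/DQ test below 6 months. Many early transplants may therefore lack a formal prior score, mainly in one group, and overlap between the groups may fall.

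### The treatment-by-CBPS interaction and the form of the Cox model hinge on separate within-stratum tests, which do not test whether effects differ, and no decision rule is stated

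*Combined protocol and SAP*

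**What the plan says.** All of this is in section 6.2 (Analysis Plan), Aim 1. Participants are ordered by CBPS and cut into strata ("It is useful at this point to select CBPS to cut points to form homogeneous strata"); neither the number of strata nor the cut points are given. Before any modelling, "we will compare survival times based on the log-rank test in Kaplan-Meier analysis", together with t-test comparisons of mean scores between treatments for "neurodevelopment and quality of life within each stratum to evaluate evidence of heterogeneity".

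Signs of heterogeneity are treated as hints of an interaction with severity, which "will be modeled in regression analyses below by including a cross products term of treatment type with CBPS". The linear models then contain treatment, the baseline value, "as well as the CBPS and if necessary the cross product of treatment type by CBPS". For survival, the Cox models "will either control for CBPS or stratify on it in the case of heterogeneity".

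The section states no significance level for the stratum tests, no rule for what counts as heterogeneity, no test of the product term once fitted, and no coding or centring of CBPS.

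**The concern.** A t-test or log-rank test inside one stratum addresses whether the effect there is zero. Whether the effect differs between strata is a separate question, answered by comparing the stratum effects with each other or by testing an interaction. With small strata, some tests will reach significance and others will not, even when the true effect is the same everywhere.

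The step is more than description, because it decides which linear and Cox models are fitted. Three things are at stake:

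- The form of the Aim 1 models depends on a noisy, data-driven screen with no stated rule.
- If the product term enters with CBPS uncentred, the treatment coefficient changes meaning.
- For survival, the response to heterogeneity does not estimate it.

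**Working it through.** **Inputs.** From section 6.2: two-sided alpha 0.05, 80 to 90 per group, 0.4 SD effect, two measurements correlated at 0.7, 28% mortality on conservative management and an increase of about 60% with transplant. Applying the alpha and group sizes to the stratum tests is an assumption; the plan gives them for power only. The number of strata K is not stated; I take 3 to 5 of similar size, with K = 2 as a check.

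**The plan's own power.** The mean of two measures has variance (1 + 0.7)/2 = 0.85, so the standardised effect is d = 0.4/√0.85 = 0.434. Power is Φ(d√(n/2) − 1.96):

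- n = 80: Φ(2.744 − 1.96) = 78.3%
- n = 90: Φ(2.910 − 1.96) = 82.9%

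This reproduces the stated 80%.

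**Chance of a mixed pattern under a constant effect.** Let p be the power in one stratum (noncentral t, n/K per arm). With K independent strata, P(mixed) = 1 − p^K − (1 − p)^K. Example with K = 5, 18 per arm, d = 0.40: p = 0.215, so P = 1 − 0.0005 − 0.298 = 70%. The d = 0.40 columns take one measure per child; the d = 0.434 columns take the mean of two.

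| K | Per arm | p, d = 0.40 | Mixed | p, d = 0.434 | Mixed |
|---|---|---|---|---|---|
| 2 | 40–45 | 42–47% | 49–50% | 48–53% | 50% |
| 3 | 26.7–30 | 30–33% | 63–67% | 34–38% | 68–71% |
| 4 | 20–22.5 | 23–26% | 65–69% | 27–30% | 71–75% |
| 5 | 16–18 | 19.5–21.5% | 66–70% | 22–24% | 71–75% |

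Other true effects, K = 3 to 5:

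- Zero effect (p = 0.05): 14% (K = 3) to 23% (K = 5).
- d = 0.2: 30 to 38%.
- Uneven arms over five strata (4:32, 11:25, 18:18, 25:11, 32:4): 59% at d = 0.40, 64% at d = 0.434.

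In 20,000 simulated trials per setting, one joint treatment-by-stratum test was positive in 4.8 to 5.2%.

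**From screen to claim.** In simulations with a constant effect (0.40 or 0.434 SD, K = 3 or 5), a mixed pattern followed by a product term significant at 0.05 occurred in only 4 to 5% of trials.

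**Log-rank tests.** Reading 60% as relative, mortality goes from 28% to 44.8%, with hazard ratio ln(0.552)/ln(0.72) = 1.81. Deaths per stratum are D = (N/K)(0.28 + 0.448), where N is the group size, and power is Φ(ln 1.81 × √(D/4) − 1.96). For K = 5 and N = 90, D = 13.1 and power is 19%. Over K = 3 to 5, power is 17 to 28% and P(mixed) 57 to 65%. If the change were a 60% reduction (to 11.2%), P(mixed) would be 70 to 79%.

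**Uncentred product.** In a model with treatment, CBPS and their product, the treatment coefficient is the effect at CBPS = 0. Compared with the effect at mean CBPS, its standard error is larger by √(1 + m²/s²), where m and s² are the mean and variance of CBPS (taken as alike in both arms). The spread of CBPS is an assumption:

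- Even over 0.1 to 0.9: m = 0.5, s² = 0.64/12 = 0.0533, ratio √5.69 = 2.39. At n = 80, 2.744/2.39 = 1.15, so power falls from 78% to 21%; at n = 90, from 83% to 23%.
- Even over 0.25 to 0.75: s² = 0.25/12 = 0.0208, ratio √13 = 3.61, power 12 to 13%.

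Simulation with CBPS on 0.1 to 0.9 agrees: from 73–81% to about 20%.

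**Survival branch.** Stratifying a Cox model on CBPS lets each stratum have its own baseline hazard but still estimates one treatment hazard ratio. The general sentence on heterogeneity promises a product term; the Cox sentence names only adjustment or stratification.

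**The case against.** The strongest defence is that the stratum tests are a preliminary look. The plan treats them as hints, which are then modelled by a product term, so the interaction is estimated in a regression and not declared from the strata. Nor does the plan say that a mix of significant and non-significant strata is the criterion; the investigators could compare the stratum mean differences themselves.

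Much of this stands. A reader might infer that a uniform benefit would be reported as severity-dependent in about 70% of trials. The documents do not support that: the 63 to 75% is how often a significance-based screen could bring in the term, and if the term is then tested at 0.05, a false claim arises in 4 to 5%. A reader might also infer that the survival model would show a spurious dependence on severity. It could not, because a stratified Cox model yields one common hazard ratio. The percentage is also conditional on an effect near 0.4 SD and on 3 to 5 similar strata. Uneven arms are plausible, since Table 2 shows peak ammonia above 200 in 98% against 74%, and CPSD in 12 against 1. Lastly, the plan does not say CBPS is left uncentred; it is silent.

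The defence does not remove the gate. The product is fitted only "if necessary the cross product of treatment type by CBPS", no other basis for that decision is given, and no test of the fitted term is specified. A real interaction could therefore go untested as easily as an absent one could be modelled.

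**Conclusion.** The concern holds in this form: the plan uses tests that cannot answer the heterogeneity question to decide the form of its models, and states no rule for reading them. If significance patterns are the evidence, a constant 0.4 SD effect would look heterogeneous in about 63 to 75% of trials. This assumes 3 to 5 similar strata, 80 to 90 per group and alpha 0.05 in each stratum. With two strata the figure is about 49 to 50%, and with no effect (3 to 5 strata) 14 to 23%. One interaction test would be positive in 5%.

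The harm is data-driven model choice, not a 63 to 75% rate of false interaction claims. If CBPS is left uncentred, there is a second harm: the treatment coefficient refers to the edge of the probability scale, with power of roughly 12 to 23% under the assumed CBPS spreads. In the survival branch, stratification does not address the heterogeneity that prompted it. This should be corrected before analysis.

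**What to change.** In section 6.2:

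1. Drop the within-stratum t-tests and log-rank tests as the basis for choosing models.
2. Pre-specify, for each outcome, one test of treatment by centred CBPS (1 df) in the linear and the Cox models, with its significance level. If the Cox model is also stratified to allow different baseline hazards, keep the product term in it.
3. Report the average treatment effect as the main result whatever the interaction test shows, since a non-significant test does not establish a uniform effect.
4. Fix the number of strata and the cut points before outcomes are examined, and present stratum estimates with confidence intervals as description only.

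The cost is a change of wording; data and software stay the same.
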